9.1 Analyses and Reporting

Data will be analyzed and reported after all 30 patients have enrolled in the clinical trial and have received 2 cycles of treatment. All subsequent data collected will be analyzed and reported in a follow-up clinical report.

9.2 Data and Safety Monitoring

In addition to the requirements for adverse event reporting as outlined in section 7.2, this protocol is also subject to the UC Davis Cancer Center's (UCDCC) Data and Safety Monitoring Plan. The UCDCC is committed to pursuing high-quality patient-oriented clinical research and has established mechanisms to ensure both scientific rigor and patient safety in the conduct of clinical research studies. The UCDCC relies on a multi-tiered committee system that reviews and monitors all cancer clinical trials and ensures the safety of its participants, in compliance with institutional and federal requirements on adverse event (AE) reporting, verification of data accuracy, and adherence to protocol eligibility requirements, treatment guidelines, and related matters. The Scientific Review Committee (SRC) assumes overall

oversight of cancer studies, with assistance and input from two independent, but interacting, committees: the Quality Assurance Committee and the Data Safety Monitoring Committee. A multi-level review system strengthens the ability of the UCDCC to fulfill its mission in conducting high quality clinical cancer research.

As per University of California Davis Cancer Center (UCDCC) Clinical Trials Support Unit (CTSU) SOP AM 506: Protocol Specific Meetings, the principal investigator (PI) and clinical research coordinator (CRC) meet at least monthly for ongoing study information, to discuss patient data and adverse events and to determine if dose escalation is warranted, when applicable. Representatives from all participating centers will be included via conference call, as well as representatives from the drug provider or financial sponsor if necessary. The call will update participants on the current status of the trial, any serious adverse events encountered will be discussed, and appropriate action taken. In between these regularly scheduled conference calls, investigators will be informed of any serious adverse events via email.

According to the UCDCC Data and Safety Monitoring Plan (DSMP), any new serious adverse events related to the drugs being used on this trial are reviewed monthly by the UCDCC Data and Safety Monitoring Committee (DSMC) and any applicable changes to the study are recommended to the PI, if necessary.

The UCDCC Scientific Review Committee (SRC) determines if a UCDCC Data and Safety Monitoring Board (DSMB) is required. If required, the DSMC will appoint a DSMB. The DSMB is responsible for reviewing study accrual logs, adverse event information and dose escalation meeting minutes (where applicable) to ensure subject safety and compliance with protocol defined guidelines.

10 Study monitoring and auditing

10.1 Investigator responsibilities

Investigator responsibilities are set out in the ICH guideline for Good Clinical Practice (GCP) and in the US Code of Federal Regulations.

Investigators must enter study data onto CRFs or other data collection system. The Investigator will permit study-related monitoring visits and audits by Celgene or its representatives, IRB/EC review, and regulatory inspection(s) (e.g., FDA, EMEA, TPP), providing direct access to the facilities where the study took place, to source documents, to CRFs, and to all other study documents

The Investigator, or a designated member of the Investigator's staff, must be available at some time during monitoring visits to review data and resolve any queries and to allow direct access to the subject's records (e.g., medical records, office charts, hospital charts, and study related charts) for source data verification. The data collection must be completed prior to each visit and be made available to the Celgene representative so that the accuracy and completeness may be checked.

11 Biostatistical Analysis

11.1 Overview

This is a Phase II trial designed to assess the efficacy and toxicity of the combination of lenalidomide with rituximab in patients previously untreated follicular NHL.

11.2 Datasets to be analyzed

The primary study endpoint is response to therapy (defined as a CR, nCR, or PR of 4 months). The secondary end points (time to progression, tolerability, duration of response and overall survival will be measured from the time of entry into the clinical trial.

Toxicity information recorded will include the type, severity, time of onset, time of resolution, and the probable association with the study regimen. Tables will be constructed to summarize the observed incidence by severity and type of toxicity.

11.3 Statistical Methodology

30 patients will be treated with rituximab and lenalidomide at indicated dose levels. Objective response (CR +PR) will be monitored using Simon's optimal 2-stage design. This study design is optimal in that sense that it minimizes the expected sample size among competing designs. The OR rate of rituximab naïve follicular lymphoma patients treated with rituximab alone is approximately 60%. A 20% increase in the objective response rate with the addition of lenalidomide to 80% in this treatment naïve patient population would justify evaluation of this regimen in larger, more definitive trials. We assume a one-sided type I error rate of 5% and desire at least 80% power to conclude that this regimen elicits and objective response rate significantly greater than 60% if the true response rate of this regimen is 60% or higher. Under these assumptions, if 11 or fewer OR's are observed in the first 26 patients, the principal investigator may conclude that regimen is insufficiently active to warrant further study. Otherwise, accrual will continue to a total of 30 patients. If 15 or more OR's are observed in 30 patients, this regimen will be deemed sufficiently active to warrant further study. Given the relatively small sample size the additional study in patients receiving radiation therapy would be considered exploratory. Any documented response would be considered "significant" and warrant further study.

Analysis Plan:

Continuous variables (e.g., age, hematology values) will be summarized using the mean (s.d.) or median (range). Frequency tables will be used to summarize categorical variables. Logistic regression will be used to assess the impact of patient characteristics (e.g., low/high LDH) on the objective response rate. The distribution of time-to-event endpoints (e.g., CR duration, overall survival) will be estimated using the method of Kaplan and Meier. Comparison of time-to-event endpoints by important subgroups of patients will be made using the logrank test. Cox (proportional hazards) regression will be used to evaluate multivariable predictive models of time-to-event outcomes.

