4.1 Introduction

Despite the availability of multiple therapeutic modalities and a high response rate to initial therapy, most patients with low grade non-Hodgkin lymphoma (NHL) will develop recurrent or refractory disease and most ultimately die from lymphoma-related complications. Chemotherapy and radiation therapy have clearly provided benefit to patients with these disorders. It is evident, however, that these agents are limited in their potential for cure of patients with indolent lymphoma, and thus new approaches are under investigation. The monoclonal antibody rituximab (directed against the B-cell antigen CD20) has been shown to be useful in the treatment of relapsed patients with low grade NHL for which it received Food and Drug Administration (FDA) approval. In a pivotal trial of 166 patients with relapsed low grade NHL, a response rate of 48% was observed (approximately 60% in the follicular histologies), with a median time to progression (TTP) of 12 months in responders. A higher response rate was observed in patients receiving rituximab as second-line therapy (compared to those patients following three or more prior chemotherapy regimens). In low-grade NHL patients who initially respond (time to progression of at least 6 months) and then relapse after single agent rituximab therapy, an overall response rate of 40% has been reported following retreatment, with median TTP of about 18 months after the second administration. Subsequent studies of rituximab have evaluated its utility as a single agent in various other subtypes of NHL, such as diffuse large B-cell and mantle cell, as well as in combination with numerous chemotherapy regimens. Rituximab has been widely adopted by oncologists as a well-tolerated and active agent in NHL, and most lymphoma patients receive it at some point in their course either as a single agent, or in combination with chemotherapy.

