6.1 Treatment Schedule

Lenalidomide capsules will be taken orally in the morning each day on days 1 - 21, followed by 7 days of no therapy of each 28-day cycle. Rituximab will be given by intravenous infusion weekly for 4 weeks beginning on day 15 of treatment start, thus on days 15, 22 of cycle 1 and days 1 and 8 of cycle 2.

Following cycle one, therapy with lenalidomide will continue in 28-day cycles, until there is disease progression, unacceptable toxicity or the patient chooses to withdraw from therapy. Lenalidomide may be discontinued after twelve cycles if complete response demonstrated, per physician and patient discretion. Additional course of rituximab will be administered if CR not attained after cycle 4, to be administered during cycle 5 on days 1, 8, 15 and 22. The patient must see the study physician before the next cycle may begin. There will be a +/-3 day window for study visits and procedures after completion of cycle one.

Dosing regimen

The planned maximum dose of lenalidomide for investigation is 20 mg daily, days 1-21 of a 28 day cycle. Dosing will be in the morning at approximately the same time each day. Lenalidomide may be taken orally either with a full or an empty stomach.

Due to the uncertain amount of re-absorption of lenalidomide, there will be no re-dose for lenalidomide if the patient vomits the pills.

Lenalidomide capsules should be swallowed whole, and should not be broken, chewed or opened.

If a dose of lenalidomide is missed, it should be taken as soon as possible on the same day. If it is missed for the entire day, it should not be made up.

Patients who take more than the prescribed dose of lenalidomide should be instructed to seek emergency medical care if needed and contact study staff immediately.

Prophylactic anti-coagulation is required during lenalidomide treatment. See Section 6.5.1.2.

Rituximab 375 mg/m2/week will be administered by IV infusion starting on day 15 from start of treatment and will continue weekly for 4 weeks (a total of four doses). The course of rituximab will be repeated if CR not attained after cycle 4. It will be administered at 375 mg/m2 weekly during cycle 5 on days 1, 8, 15 and 22.

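### Responses first reached after the second rituximab course count against a 60% rituximab-alone benchmark of unstated schedule, so an excess over 60% cannot be credited to lenalidomide alone

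*Combined protocol and SAP*

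**What the plan says.** Section 11.3 (Statistical Methodology) takes its null from a historical rate: "The OR rate of rituximab naïve follicular lymphoma patients treated with rituximab alone is approximately 60" per cent. It gives no number of doses or courses and no assessment window for that figure. The target is worded as "A 20% increase in the objective response rate with the addition of lenalidomide to 80" per cent. The error rates are set by "We assume a one-sided type I error rate of 5% and desire at least 80% power". The decision rule stops for inactivity "if 11 or fewer OR's are observed in the first 26 patients", and otherwise declares the regimen active "If 15 or more OR's are observed in 30 patients".

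The first rituximab course is four weekly doses, from cycle 1 day 15 to cycle 2 day 8. Section 6.1 then says: "Additional course of rituximab will be administered if CR not attained after cycle 4". That course is given on days 1, 8, 15 and 22 of cycle 5, and the synopsis and Section 5.3 agree. Patients in PR and patients with stable disease both qualify.

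Response is assessed after every two cycles (Section 2, footnote 7). Sections 5.2.1, 11.2 and 11.3 set no latest time for reaching a response and do not separate responses before the second course from those after it. On the first report, Section 9.1 says: "Data will be analyzed and reported after all 30 patients have enrolled in the clinical trial and have received 2 cycles of treatment". Later data go into a follow-up report.

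Section 4.1 gives about 60% for follicular histologies in a pivotal trial of rituximab in relapsed disease. It treats repeat rituximab as a separate step: "an overall response rate of 40% has been reported following retreatment".

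**The concern.** Crediting a gain over rituximab alone to lenalidomide requires the rituximab to be the same on both sides. Here a patient with stable disease after cycle 4 gets four further doses and can become a responder at a later scan. If the 60% comes from one course, the benchmark had no such opportunity. The response rate to be expected with an inert lenalidomide would then lie above 60%, and the trial could support a statement about lenalidomide that is partly about rituximab exposure.

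This is a different question from whether 60% is the right one-course rate for this population. It would remain if that figure were exact.

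**Working it through.** **1. The plan's own rule.** Inputs from Section 11.3: null 60%, target 80%, stop at 11 or fewer of 26, success at 15 or more of 30. The exact two-stage binomial probability of success is 0.899 at 60% and 0.9999 at 80%. The stated 5% error is not reproduced, because 15 of 30 is a 50% bar set below the 60% null. To see the present issue separately, a cut-off that does hold 5% is needed. With 30 patients that is 23 or more: P(X ≥ 23 | 30, 0.60) = 0.044, whereas 22 or more gives 0.094. The first-stage stop does not change these figures to the precision shown.

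**2. Who can change the objective response rate.** At 60%, 30 × 0.40 = 12 patients are expected not to respond to the first course. Only those still on treatment at cycle 5 receive the second. A patient already in PR is already counted, so retreatment can change only that patient's CR status.

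**3. The rate with no lenalidomide effect.** Let c be the share of all first-course non-responders who convert after the second course. It is the product of the share still on treatment at cycle 5 and the conversion rate among them. Then:

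rate = 0.60 + 0.40 × c

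The documents give no value for c. The range below is an assumption.

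| c (assumed) | Conversions among 12 | Rate with no lenalidomide effect | P(≥ 23 of 30) | P(success), plan's rule |
|---|---|---|---|---|
| 0 | 0 | 60% | 4.4% | 89.9% |
| 2.5% | 0.3 | 61% | 5.5% | 91.8% |
| 5% | 0.6 | 62% | 6.8% | 93.4% |
| 10% | 1.2 | 64% | 10.2% | 95.9% |
| 20% | 2.4 | 68% | 20.8% | 98.7% |

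The pattern does not depend on a single-stage cut-off. For the true Simon optimal design at 60% versus 80% (stop at 7 or fewer of 11, success at 31 or more of 43), the error is 4.9% at 60%, 12.4% at 64% and 25.7% at 68%.

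**4. Whether late responses reach the first report.** Accrual is planned over 2 years (synopsis). Assume it is even over 730 days and that the Section 9.1 cut-off falls when the last patient reaches day 56. The scan after cycle 6, the first after a second course, is at day 168. The share of patients past it is (730 + 56 − 168)/730 = 0.85, about 25 of 30. If the 4 months in Section 11.2 is a required duration, taken as 120 days, the share becomes (730 + 56 − 288)/730 = 0.68, about 20 of 30. These counts cover all patients; only the non-responders among them can alter the objective response rate.

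**The case against.** **The one-course benchmark is an inference.** Section 11.3 gives no schedule for the 60%. Section 4.1 supports one course by reporting retreatment separately, but its 60% is in relapsed patients. This stands, and it makes the point conditional.

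**The size is assumed.** The only retreatment figure in the documents, 40%, comes from patients who responded, went at least 6 months to progression and then relapsed. The patients who matter here did not respond to the first course and are re-dosed about 11 weeks after it ended (day 36 to day 113), when rituximab may still be detectable (Section 5.3.2.2: 3 to 6 months). Some will have stopped for progression or lack of effect (Section 6.7). A reader might put c at 40% and infer a 76% null passed 57% of the time at 23 of 30. That needs every non-responder still on treatment and a rate from a different population; the documents support neither.

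**The boundary error dominates.** Under the plan's own rule, conversion at the assumed rates moves the chance of success only from 89.9% to between 91.8% and 98.7%. This stands. Correcting the boundary would leave the present issue in place, and it would then bear on the decision.

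**The decision concerns the regimen.** The go rule is about the regimen, which includes the second course, and a single-arm screening trial cannot isolate lenalidomide in any case. A reader might infer that the decision endpoint should be replaced by response at the end of cycle 4. The documents do not require that. Such a landmark would drop late responses on continuing lenalidomide and set a week-16 rate against a benchmark whose window is unknown, which could bias the comparison the other way. What remains is that Section 11.3 words the gain as lenalidomide's.

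**Complete response.** It is tempting to say the CR part of the primary objective is biased more, since PR patients are retreated too. Section 11.3 sets no CR benchmark, so there is no comparison to bias.

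**Conclusion.** The point holds as a limit on attribution. If the 60% reflects one rituximab course and any non-responder converts on the second, the response rate with no lenalidomide effect exceeds 60%. At the assumed conversion rates the excess is 1 to 8 percentage points, and the false-positive rate of a cut-off valid at 60% rises from 4.4% to between 5.5% and 21%. These are illustrations over an assumed range, not estimates from the documents. They also use a cut-off that the plan does not contain; the plan's cut-off needs its own correction. The documents do not show that the bias is large, and they do not show that the regimen-level go/no-go decision rests on the wrong quantity.

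**What to change.** In Section 11.3:

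- State the rituximab schedule (courses and doses) behind the 60%, and its assessment window if known.
- Keep the regimen's overall objective response as the go/no-go quantity.
- Add a pre-specified objective response rate with an exact confidence interval, counting responses whose criteria are first met by the end-of-cycle-4 assessment, before any cycle 5 rituximab. Confirmation may fall later. Name this as the like-for-like comparison with 60%.
- State that an excess driven by responses first reached after the second course supports the whole regimen and is not attributed to lenalidomide.

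Treatment, visits and scans do not change, because response is already assessed after every two cycles. The cost is a few sentences and one extra analysis. Its rate may be lower than the best-response rate, and it may miss slow responders, which is why it should sit beside the overall rate and not replace it. The 15-of-30 boundary must be corrected separately.

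### The 15-of-30 success boundary lies below the plan's own 60% null, so the rule's type I error is about 90%, not 5%, and 30 patients cannot give 80% power at 5%

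*Combined protocol and SAP*

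**What the plan says.** All the relevant text is in section 11.3 (Statistical Methodology) of the combined protocol and SAP.

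- Design: "Objective response (CR +PR) will be monitored using Simon's optimal 2-stage design". The section adds: "This study design is optimal in that sense that it minimizes the expected sample size among competing designs".
- Null rate: "The OR rate of rituximab naïve follicular lymphoma patients treated with rituximab alone is approximately 60" per cent.
- Target rate: "A 20% increase in the objective response rate with the addition of lenalidomide to 80% in this treatment naïve patient population would justify evaluation".
- Error rates: "We assume a one-sided type I error rate of 5% and desire at least 80% power". The conclusion to be supported is a response rate "significantly greater than 60% if the true response rate of this regimen is 60% or higher".
- First-stage rule: the investigator may judge the regimen too inactive "if 11 or fewer OR's are observed in the first 26 patients". Otherwise accrual goes on to 30.
- Final rule: "If 15 or more OR's are observed in 30 patients, this regimen will be deemed sufficiently active to warrant further study".

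The section presents both boundaries as following from these assumptions. Section 5.3 (Overall design) repeats the total of 30 patients.

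**The concern.** The success boundary is an observed rate of 50%, yet passing it is supposed to show a rate above 60%. The boundary is on the wrong side of the null. The sentence that should place power at the 80% target places it at 60%, which is the null itself. The interim look comes when 26 of 30 patients have been treated, with a 42% threshold (11/26), so it can do little to limit exposure to an inactive regimen and does not look like a design chosen to minimise expected sample size.

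This is the only formal efficacy rule for the main cohort. If it is followed as printed, a regimen no better than rituximab alone would nearly always be carried forward, and one somewhat worse would be carried forward more often than not. A pass near the boundary would say nothing in favour of adding lenalidomide.

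**Working it through.** **Inputs (all from section 11.3).** Null p0 = 0.60; target p1 = 0.80; one-sided alpha 0.05; power at least 0.80; stage 1: n1 = 26, stop at 11 or fewer; total N = 30; success at 15 or more.

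**Step 1. The printed rule at the null.** With X1 responses among the first 26 and X2 among the last 4,

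P(declare active | p) = Σ over x = 12 to 26 of P(X1 = x) × P(X2 ≥ 15 − x).

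At p = 0.60:

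- X1 ≥ 15, already a success: 0.6737
- X1 = 14: 0.1270 × 0.9744 = 0.1237
- X1 = 13: 0.0912 × 0.8208 = 0.0748
- X1 = 12: 0.0564 × 0.4752 = 0.0268
- Sum: **0.899**, against the stated 0.05

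This treats the stage-1 stop as binding. The text says only that the investigator may stop; if the stop is ignored, the figure is P(Bin(30, 0.60) ≥ 15) = 0.903.

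**Step 2. The printed rule at other true rates.**

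| True response rate | P(declare active) |
|---|---|
| 34% | 0.050 |
| 48% | 0.477 |
| 50% | 0.565 |
| 55% | 0.763 |
| 60% | 0.899 |
| 80% | 0.9999 |

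The rule has a 5% error rate only if the null is about 34%, a value that appears nowhere in the section. An observed 15/30 has an exact 90% confidence interval of 34% to 66%, which contains 60%.

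**Step 3. The interim look.** P(stop | 0.60) = P(Bin(26, 0.60) ≤ 11) = 0.052. Expected sample size under the null = 26 + 4 × (1 − 0.052) = 29.8 of 30.

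**Step 4. What the stated assumptions require.** An exhaustive exact search for 60% against 80%, alpha ≤ 0.05 and power ≥ 0.80 gives:

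| Design | Stop at stage 1 | Success | Alpha | Power | Expected N at 60% |
|---|---|---|---|---|---|
| Simon optimal | ≤ 7 of 11 | ≥ 31 of 43 | 0.0489 | 0.802 | 20.5 |
| Simon minimax | ≤ 8 of 13 | ≥ 26 of 35 | 0.0499 | 0.808 | 20.8 |
| Smallest single-stage | none | ≥ 27 of 36 | 0.0449 | 0.832 | 36 |

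The printed boundaries match none of these.

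**Step 5. What 30 patients can do.** Single-stage exact values at N = 30:

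| Success count | Alpha at 60% | Power at 80% |
|---|---|---|
| ≥ 21 | 0.176 | 0.939 |
| ≥ 22 | 0.094 | 0.871 |
| ≥ 23 | 0.0435 | 0.761 |
| ≥ 24 | 0.017 | 0.607 |

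A search over all two-stage rules with N = 30 finds nothing better than 0.761 power with alpha at or below 5%.

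**Step 6. Could one figure be a misprint?** Keeping 11/26 and moving only the final boundary gives the same pairs as step 5: 23 meets alpha but not power, and 22 meets power but not alpha. Keeping the stop at 11 and success at 15 of 30 while changing n1 fails too: at n1 = 14, alpha is 0.040 but power 0.448; at n1 = 16, power is 0.798 but alpha 0.167. No single change repairs the design.

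**The case against.** The best defence is that 60% was meant as the rate at which power is computed. The power sentence reads that way, and the printed rule does have about 90% power there. But the section names 60% as the rituximab-alone rate and as the rate to be exceeded, and gives no lower null. Supplying one by assumption does not help much: 35% gives alpha 6.3% and 40% gives 17.2%. The boundaries also match no Simon optimal or minimax design for the other pairs tried (35/60, 35/55, 30/50).

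Second, 30 patients is nearly enough. That is fair. The exact shortfall is 80 − 76.1 = 3.9 points, and approximate single-stage formulas come closer: about 33 patients by the normal approximation (power 76.5% at 30) and 32 by the arcsine (78.1% at 30). The sample size is the smaller part of the problem. No approximation rescues the 15-of-30 boundary.

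Third, the consequences should not be overdrawn. At a true rate of 48% the rule passes the regimen slightly less than half the time, so an inferior regimen passes more often than not only from roughly 50% upward. A high count would still be informative: 23 or more of 30 rejects 60% at one-sided 5% whatever the rule calls it. The front-line study cited in the background had an 86% response rate, so a high count may well occur. All of this stands, but it concerns what the data might show. It does not make the printed rule a 5% test of 60%.

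**Conclusion.** The concern holds. Tested against the section's own hypotheses, the rule has a type I error of 89.9% (90.3% if the early stop is not enforced), about 18 times the stated 5% (0.899/0.05). The interim look stops a null regimen 5.2% of the time and saves 0.2 patients on average, so the optimality claim is wrong. The power sentence names the null where the target belongs. With 30 patients and alpha at or below 5%, power at 80% cannot exceed 76.1%.

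These results assume independent responses, 30 evaluable patients, response counted as CR plus PR, and 60% as a fixed null. They rest on no figure from outside section 11.3. The boundary error is the serious one and must be corrected; the power shortfall is real but modest.

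**What to change.** Keep 30 patients and rewrite the decision rule in section 11.3:

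1. Declare the regimen active only if 23 or more of 30 patients respond. State the properties as one-sided alpha 0.043 and power 76% at a true rate of 80%.
2. Correct the power sentence so that it refers to a true rate of 80% or higher.
3. If the first look can still be set, move it early. For example, stopping at 7 or fewer of the first 13, with success at 23 of 30, gives alpha 0.043, power 0.758, a 0.43 chance of stopping at 60%, and an expected sample size of 13 + 17 × (1 − 0.426) = 22.8. Otherwise drop the 26-patient look and the optimality claim.
4. If 80% power matters more than 5% alpha, state alpha as 10% and set success at 22 or more; with the same 13-patient look this gives alpha 0.091 and power 0.864.
5. If both 5% and 80% must be kept, more patients are needed: a maximum of 35 under the minimax design or 43 under the optimal design.

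Options 1 to 4 need no additional patients. Their cost is a lower stated power or a higher stated alpha. The protocol was final in 2010 and this version is dated 2018. If responses are already known, label the corrected boundary as set after the fact and report the result under the printed rule beside it.

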5.3 Overall design

The study is a phase II clinical trial with all patients to be accrued at UCD Cancer Center and other participating centers. All patients who are eligible will receive both lenalidomide and rituximab.

- Lenalidomide will be started at 20 mg daily, days 1-21 of a 28 day cycle.
- A total of 30 patients will be evaluated in this study.
- Rituximab 375 mg/m2/wk x 4 weeks, to begin on day 15 of cycle 1. After 4 cycles of therapy if a patient has not achieved a CR, the patient will be given a second course of Rituximab, on days 1, 8, 15 and 22 of cycle 5.

Patients who progress through this combination will be offered optional participation in a radiotherapy cohort. Up to 10 patients who consent will continue lenalidomide and receive local radiotherapy to a single target lesion.

- Lenalidomide will be continued at the patient's most recent dose daily, days 1 21 of a 28 day cycle.
- Radiotherapy will be delivered to a single involved site to a dose of 20 Gy over 5 daily fractions of 4 Gy each, day 1-5, using electron or photon beams with a conventional linear accelerator.

Investigational Drugs

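### The response regression in 30 patients names no sparse-data method: at the 80% target the LDH odds ratio would be non-finite in about 8–30% of trials (high-LDH share assumed)

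*Combined protocol and SAP*

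**What the plan says.** Section 5.3 fixes the size of the study: "A total of 30 patients will be evaluated in this study". Section 11.3 sets the reference response rate, "The OR rate of rituximab naïve follicular lymphoma patients treated with rituximab alone is approximately 60" per cent, and the target: "A 20% increase in the objective response rate with the addition of lenalidomide to 80% in this treatment naïve patient population". Section 4.6 cites an 86% response rate among 28 patients for the same combination given front-line.

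The Analysis Plan within Section 11.3 then states "Logistic regression will be used to assess the impact of patient characteristics (e.g., low/high LDH) on the objective response rate". For time-to-event outcomes it adds "Cox (proportional hazards) regression will be used to evaluate multivariable predictive models of time-to-event outcomes".

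The plan gives no covariate list, no limit on the number of parameters, no projected numbers of progressions or deaths, and no exact, penalised or other fallback for sparse tables. The share of patients with high LDH is not given. Section 11.3 calls the radiotherapy cohort exploratory but does not say so of the regression models.

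**The concern.** A logistic model draws its information from the smaller outcome group. If the regimen performs as hoped, that group is the non-responders, and there are few of them. Splitting about 6 patients by a two-level factor can leave one cell of the 2 × 2 table empty. Maximum likelihood then has no finite solution: software prints a huge coefficient with a huge standard error, or stops.

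The problem grows as the regimen works better, so the method is weakest in the scenario that the trial aims for. At stake is whether the planned response-by-characteristic results can be reported at all, and how accurate they are when they can. The primary response rate and the decision rule are not at stake.

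**Working it through.** **The plan's own figure.** None is stated for the regression models, so there is nothing to reproduce. (The two-stage cut-offs in the same section do not reproduce the stated 5% type I error. That is a separate matter and does not enter here, where only N = 30 and the response rates are used.)

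**Inputs.** N = 30 (Section 5.3). Response rate p = 0.80 (target, Section 11.3), 0.60 (reference, Section 11.3) or 0.86 (cited study, Section 4.6). Share with high LDH, q: not in the documents, assumed 0.20 to 0.50.

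**Expected non-responders.** 30 × 0.20 = 6 at the target, 30 × 0.40 = 12 at 60%, and 30 × 0.14 = 4.2 at 86%.

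**Probability of an empty cell, no association.** The four cell probabilities are qp, q(1−p), (1−q)p and (1−q)(1−p). By inclusion–exclusion,

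P(empty) = Σ(1−c_i)^30 − Σ(1−c_i−c_j)^30 + Σ(1−c_i−c_j−c_k)^30.

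For p = 0.80 and q = 0.20 the cells are 0.16, 0.04, 0.64 and 0.16. The single-cell terms are 0.96^30 = 0.2939, 0.84^30 = 0.0054 (twice) and 0.36^30 ≈ 0, total 0.3046. The pair terms are 0.80^30 = 0.0012 (twice) plus a negligible remainder, total 0.0025. The triple terms are negligible. The result is 0.3046 − 0.0025 = 0.302. The other scenarios in the same way:

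| Share with high LDH (assumed) | 60% response | 80% response | 86% response |
|---|---|---|---|
| 20% | 10% | 30% | 45% |
| 30% | 2% | 17% | 31% |
| 40% | 0.6% | 10% | 24% |
| 50% | 0.3% | 8% | 22% |

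If only 10% had high LDH, the figure at 80% response would be 59%.

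**With exactly 6 non-responders.** The hypergeometric probability for 6 high-LDH patients is C(24,6)/C(30,6) = 134,596/593,775 = 23%. It is 9% for 9 such patients, 3% for 12 and 2% for 15. Much of the risk at shares of 40–50% therefore comes from trials with fewer than 6 non-responders. At 80% response, 4 or fewer occur with probability 0.255.

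**With a true effect.** For odds ratios of 2 to 5 against high LDH at 80% response, the probability of an empty cell is 12–18% at a 20% share, 9–10% at 30%, 9–17% at 40% and 12–28% at 50%.

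**Bias of the finite estimates.** At 80% response, a 20% share and a true log odds ratio of −1.37 (odds ratio about 0.25), simulation gives a mean of −1.49 for the finite maximum-likelihood estimates and −1.38 for Firth. As a check, all tables were enumerated at an odds ratio of exactly 0.25 (log odds ratio −1.39). At a 20% share the response probabilities are 0.591 (high LDH) and 0.852 (low LDH), and the means are −1.52 (finite maximum likelihood) and −1.40 (Firth). At 30% they are −1.43 and −1.38. At 40% and 50% the finite maximum-likelihood mean moves the other way (−1.32 and −1.16), because the tables most extreme in the true direction have empty cells and drop out. Firth gives −1.36 and −1.32.

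**What the estimates look like.** Suppose all 6 high-LDH patients respond and the low-LDH group has 18 responders and 6 non-responders. The ordinary odds ratio is infinite. Firth, which here equals adding 0.5 to each cell, gives (6.5 × 6.5)/(0.5 × 18.5) = 4.6. Precision is poor even without an empty cell. With 7 responders and 2 non-responders (high) against 17 and 4 (low), the odds ratio is (7 × 4)/(2 × 17) = 0.82. The standard error of its logarithm is √(1/7 + 1/2 + 1/17 + 1/4) = 0.98, and the 95% interval is about 0.12 to 5.6.

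**The case against.** Section 11.3 says only logistic regression. Exact and Firth-penalised fits are both logistic regression, so the present sentence does not exclude them and no failure is written into the plan. That is fair as far as it goes. But the unqualified term ordinarily means maximum likelihood, and an analyst following it would fit that.

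The frequency rests on an LDH share that the documents do not give, and LDH is only an example. At a 60% response rate the risk is 10% or less over the same range of shares. This stands, and is why a range is reported. A reader might infer that the LDH analysis would usually fail. The figures do not show that: at the 80% target the risk exceeds one half only if high LDH is rare, at about 10%.

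A reader might also infer that empty cells would produce false predictors of response. They would not, at least through the Wald test. In the 6-of-6 against 18-of-24 example the standard error is about 12,000 and the Wald p-value 0.999, and the empty cell would show in a frequency table. The harm is a missing or unusable estimate and, in some settings, a moderately biased one.

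Finally, no listed objective concerns baseline predictors, and the go/no-go rule uses response counts alone. This also stands and keeps the point minor.

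**Conclusion.** The point holds as a minor improvement to a secondary analysis. With 30 patients and about 6 expected non-responders, the ordinary odds ratio for the plan's own example would be infinite or not estimable in about 8–30% of trials at the 80% target, 22–45% at 86% response and 0.3–10% at 60%. These figures assume that 20–50% of patients have high LDH and that LDH and response are unrelated.

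The bias away from the null is modest. It is shown for a 20% high-LDH share and an odds ratio near 0.25, and should not be generalised: at shares of 40–50% the mean of the finite estimates falls short of the true effect.

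A reader might extend the argument to the Cox models. The documents do not support that. The number of non-responders says nothing about a Cox model, whose information comes from progressions and deaths. The plan projects neither and does not state how many covariates would be used. All that can be said is that each outcome has at most 30 events and that no covariate limit is set, which is a general caution and not a demonstrated error.

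**What to change.** In the Analysis Plan of Section 11.3, specify Firth-penalised (or exact) logistic regression for objective response, one covariate at a time, with profile-likelihood or exact confidence intervals. Show the 2 × 2 counts beside each estimate. If a whole margin is empty (no high-LDH patients, or no non-responders), report that the association cannot be assessed, since no method supplies the missing information.

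The cost is a sentence of text and standard software, with no change to data collection, sample size or decision rule. The one loss is a mutually adjusted response model. About 6 non-responders support roughly one parameter by the usual rule of thumb, so little is given up.

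As an optional courtesy, the Cox sentence could state a covariate limit once the expected numbers of progressions and deaths are known.
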